5. STUDY PROCEDURES

Activities Prior to Research PET/MR Exam

For all subjects, study staff will confirm that the subject is eligible and complies with applicable site requirements prior to starting study procedures. After the subject completes the ICF, he/she will be required to complete certain activities to participate in the study.

Pre-Screening Activities (All Subjects)

- **Verify site institutional policy(ies) for MR safety are followed.**
- **Record implant information** for subjects with implants allowable per the inclusion/exclusion that will be present during scanning (with the exception of passive dental filling/implants, surgical clips, or surgical staples)*, as follows:
 - i. Name of the device
 - ii. Manufacturer of the device
 - iii. Model Number of the device

Note: If any or all information is not available, write N/A in the applicable area(s)

- **Record subject characteristics**, as follows:
 - i. age (in years)
 - ii. gender
 - iii. weight
 - iv. height

Pre-Screen Activities for PET/CT Subjects

- **Record clinically indicated PET/CT information** (before the PET/CT scan when possible to limit delay time between PET/CT and research PET/MR exam), including start and end time of the PET/CT scan and information about injected radiotracer, as follows:
 - i. radiotracer type, dose and units, and time of injection
 - ii. clinical indication for PET/CT scanning (oncology, neurology, and/or cardiac etc.)
 - iii. date and time of PET/CT
- **Check for completeness** of acquired PET/CT images, if a subject is missing required PET/CT images, the subject may be withdrawn from the study. PET/CT images will be collected as part of the study.
- **Check for solid food or insulin administration.** If a study subject is administered insulin, solid food, or any non-water beverage prior to the PET/MR imaging that can be expected to interfere with radiotracer activity, the subject may be withdrawn from the study at the discretion of the investigator if such administration(s) could interfere with performing study procedures and/or radiotracer bioavailability during the study period.

Activities Required before Study PET/MR for All Subjects

- **Encourage subjects to empty their bladder** prior to PET/MR scanning.
- **Provide MR-safe clothing** according to participating investigational site's standard procedures, such as hospitals gowns, and isolate all non-MR compatible equipment or devices and route the devices and/or cables as required out of the magnet room.

[figure not shown]
- Provide mandatory hearing protection, as per site institutional procedure.

■ Activities during Research PET/MR Scanning and Data Acquisition

[figure not shown]
■ Subject Procedure

The site should perform research PET/MR scans during the time that the radiotracer validity time frame. Typically research PET/MR exams should be started with approximately 4 hours of radiotracer administration; however, the site may scan a subject at their discretion if the scan is expected to take place during the clinical validity window based on the investigator's expertise (not required to be within 4 hours, Fig. 1). This is to ensure sufficient radiotracer activity during the investigational procedure.

Figure 1. Study procedure for research PET/MR scans relative to clinically indicated imaging (PET/CT or PET/MR) with injected radiotracer

Symbol Legend

Clinically indicated radiotracer injection

Clinically indicated exams (such as PET/CT required for regular medical care)

Research PET/MR Procedure (Active Study Period)

*MR Safety Screening and Pre-screening activities identified in [Section 5.1 Activities Prior to PET/MR \(Pre-Screen\)](#) should be completed prior to the start of the study PET/MR scan.

The research PET/MR scan session will be performed while the subject is lying on a scan table. During this time, the subject may be asked to shift position to one side or another, lie still and to follow simple instructions such as to hold his/her breath at specified times. Subjects may be provided with a calling system that allows him or her to contact the Device Operator at any time during the scan. While the subject is in the scanner, the device operator will remain where the subject is visible (e.g. through a window) and audible (e.g. through an intercom).

The PET/MR exam may last up to a 1 hour (which includes screening and approximately 30 minutes of scanning). Start and end time of research PET/MR scanning and additional information will be recorded as per Table 2.

■ ZTE MRAC and Q Static (Q. MRAC) PET/MR Scanning Procedure

The device operator will acquire scan data using default PET/MR scan protocols, default MR-only scan protocols, and other scanning protocols optimized by the operator as appropriate for the subject's clinical state. The scan protocols and associated pulse sequences used shall be chosen by the investigator. For PET/MR simultaneous scanning, the first scan will be a whole body localizer. The user will then define n beds ($n \leq 14$). The user will have the option to insert as many MR scans at each bed position, although a MR attenuation correction scan will always be acquired first at each bed position (approximately a 30 second scan). The PET will continue to acquire data until the time set by the

operator has elapsed. The system will then automatically move to the next bed position. The user will be able to view the PET images overlaid on the MR images from each bed after it has been reconstructed.

During each scan, the operator should complete ZTE MRAC or Q Static (Q. MRAC) protocol appropriate for the subject's indication, and record the sequence used in the exam. For Q Static (Q. MRAC) scans, the site should conduct 5 non-gated MRAC acquisitions and 5 gated acquisitions for each subject around the lung/abdominal region including the diaphragm. For all scans, the device operator should attempt to complete both PET and MRI scans on the PET/MR system and to collect an image set that includes both PET and MRI images. At the end of each scan session, the device operator will record information about the device used, the time of the scan session and his/her observations in the Case Report Forms (CRFs). If the device operator is unable to collect both PET and MRI images, he or she should record the reason on the Case Report Form (CRF). The device operator will save the images and raw data.

Table 2. Characteristics recorded to the CRF during PET/MR scan sessions

Coil(s) Used	Gating device(s) used	Medical tubes wires/cables

 3.0T PET/MR CMA 3.0T HNU 3.0T UAA 3.0T LAA GEM Flex Coil 16-S, M, L Array 3.0T Split head coil PETMR 8Ch HiRes Brain Array 3.0T HD Flat GEM Table Breast Array Other, specify 	
 Respiratory bellows ECG leads Peripheral gating photopulse sensor 	
 None IV Catheterization Breathing tube Oxygen ECG Monitor Other, specify

Emergency Procedures

In the event of a medical emergency, the scan will be stopped immediately and facility's emergency response plan will be followed. The subject will be provided with emergency care as needed.

The subject's care shall take precedence over any imaging associated with the study. In the event the subject experiences discomfort or wishes to stop the exam for any reason, the exam will be immediately stopped and appropriate follow up response will occur. The event will be recorded in compliance with US FDA and GE Healthcare safety reporting requirements.

Incidental Findings

The additional PET/MR procedures performed in this study are for research only and are not intended for diagnostic use. Should the device operator observe what they interpret to be a potential abnormality, the investigator will evaluate the findings and alert the patient if necessary. The investigator may recommend diagnostic exams to be performed independent of the study. No medical or diagnostic care of any kind will be rendered based on study image sets using the research PET/MR.

Activities after PET/MR Scanning

Upon completion of the exam, the device operator or those assisting him/her will assist the subject from the device and out of the scan area. Any reported safety or device issues will be recorded to the CRF up until the time the subject leaves the PET/MR suite.

After the exam is complete and the subject has left the PET/MR suite, the device operator will complete the CRF and store the image sets for the scan, which will be labeled with the subject's unique ID number. All images collected from clinical sites will be sent to the Sponsor or its delegate for investigational post-processing with the investigational technology prior to image reads.

Follow-up Visits

All patient procedures will be conducted during a single visit. No follow-up visits are required.

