3. STUDY OBJECTIVES AND ENDPOINTS

■ Purpose of the Study

The purpose of the study is to collect representative clinical images with demonstrated diagnostic image quality using ZTE MRAC and Q Static (Q. MRAC) software features. The images and summary data from this study are intended for use in regulatory submission(s).

■ Primary Objective:

To demonstrate diagnostic image quality of image sets with ZTE MRAC and Q Static (Q. MRAC) for SIGNA PET/MR in representative clinical cases of the general imaging population.

■ Secondary Objective(s):

To verify diagnostic acceptability, ease of use, and functionality of ZTE MRAC and Q Static (Q. MRAC) for SIGNA PET/MR at clinical sites.

■ Safety Objective(s):

To collect information about safety events and device issues.

■ Study Endpoints

■ Primary Endpoints:

Independent radiologist/nuclear medicine physician determination of diagnostic image quality considering all evaluable images from each subject (scored on a 5-pt Likert scale)

■ Secondary Endpoints:

Site level determination of diagnostic acceptability (Y/N) based on consensus between radiologist(s) and nuclear medicine physician(s) at the site

Ease of use per procedure rated on a 5-pt Likert scale score

Functionality rated for each feature per procedure on a binary (Y/N) performance scale

■ Safety Endpoints

Type and number of safety events (AEs and SAEs) and device issues (malfunctions, user errors, and labeling issues) will be summarized.

■ Summary of Study Design

This is a pre-market, open label, prospective, non-randomized clinical research study at one site. The study is designed to allow for sample PET/MR image collection and to demonstrate diagnostic image quality of resultant sample image sets from each participating subject. The results of this study will be analyzed according to a prospective Blinded Image Evaluation (BIE) plan and Statistical Analysis Plan (SAP) prepared by the Sponsor prior to the start of image reads. This study is run concurrently with other studies of the device conducted by the Sponsor and it is prospectively expected that the cumulative results of these studies may be used to support regulatory submissions.

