4. STUDY DESIGN

Study Population

Subjects will be enrolled that have a clinical indication for PET/CT or PET/MR with radiotracer injection prescribed for their medical care outside of the study. Sites should make reasonable attempts to ensure diversity of clinical state (including injury severity or extent of disease progression) within the enrolled population in order to achieve a sample maximally representative of the intended use population.

Number of Subjects

The study aims to acquire up to 75 clinical PET/MR image sets (up to 38 subjects will be enrolled to have a ZTE MRAC exam and the remaining 37 subjects will be enrolled to have a Q Static (Q. MRAC) exam. In the event that a subject scan does not produce images, as in the case of withdrawal or technical issues preventing scanning, additional subjects may be enrolled until the target number is achieved (not to exceed a maximum of 75 subjects during the course of the study) as described in [Section 10.2 - Sample Size Determination](#). The minimum number of necessary subjects will be enrolled to achieve the target number of datasets.

Enrollment Quota

Subjects will be enrolled based on a quota block method based on scan type (relative to the patient clinical indication for PET/CT or PET/MR). Each subject may have only one type of scan towards these quota blocks (ZTE or Q.Static MRAC), not both (Table 1).

Table 1. Target quota blocks for subject enrollment/target datasets

Scan Type	Target number of subject datasets ($N_{\text{Target}} = 30$)
ZTE MRAC	At least 30 subject scans ($N_{\text{neuro}} = 30$ to 38)
Q Static (Q. MRAC)	At least 30 subject scans ($N_{\text{body}} = 30$ to 37)

Protection of Vulnerable Subjects

Vulnerable subjects are individuals whose willingness to volunteer in a clinical investigation could be unduly influenced by the expectation, whether justified or not, of benefits associated with participation or of retaliatory response from senior members of a hierarchy in case of refusal to participate. The Sponsor shall avoid improper influence on, or inducement of, the subject, monitor, any investigator(s), or other parties participating in, or contributing to, the clinical investigation.

All investigators shall avoid improper influence on, or inducement of, the subject, Sponsor, monitor, other investigator(s), or other parties participating in, or contributing to, the clinical investigation.

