6. STUDY DATA COLLECTION AND ASSESSMENTS

Primary Assessment

Independent Reader Determination of Diagnostic Image Quality

Diagnostic image quality will be rated on a 5-pt Likert scale by at least 2 independent board certified nuclear medicine physician and/or radiologists for all evaluable image sets (including all clinically acquired MR image sets able to be successfully post-processed that are complete image sets [not from cases of withdrawal or critical deviation that could impair to the quality of data]). Independent reads will be conducted outside of the clinical care environment according to the procedures specified in the Blinded Image Evaluation (BIE) plan prepared by the Sponsor prior to the start of image reading. Identifiable subject information will be removed prior to independent reads.

Diagnostic image quality will be recorded on a 5-pt Likert scale, where ratings of ≥ 3 are considered acceptable for diagnostic use and ratings of 1-2 are considered unacceptable for diagnostic use, as follows:

1. **Unacceptable** (cannot be used for diagnostic use)
2. **Poor** (not completely suitable for diagnostic use)
3. **Acceptable** (suitable for diagnostic use but with minor defects)
4. **Good** (good suitability for diagnostic use)
5. **Excellent** (excellent suitability for diagnostic use)

The reader should record the rationale for any image scored unacceptable for diagnostic use (scores of 1 or 2). And/or provide comments in image annotation or point to the problem area in the images. Scores should be based on the entire image set, considering all available views, with the exception of the LAVA sequence used for MR-attenuation correction (which should not be considered in the evaluation for image quality).

Secondary Assessments

Site Determination of Diagnostic Acceptability

Based on consensus of at least one radiologist and at least one nuclear medicine physician at the site, diagnostic acceptability of each evaluable image set (including all clinically acquired MR image sets able to be successfully post-processed that are complete image sets [not from cases of withdrawal or critical deviation that could impair to the quality of data]).

Binary diagnostic image quality will be recorded by the site on a single CRF that includes the names and signatures of both the radiologist and nuclear medicine physician making the evaluation, as follows:

"Is the image of acceptable quality for diagnostic use? (Y/N)"

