The reader should record the rationale for any "no" answer indicating that the image is not acceptable quality for diagnostic use. And/or provide comments in image annotation or point to the problem area in the images. Scores should be based on all views included in the image set, considering all available views, with the exception of the LAVA sequence used for MR-attenuation correction (which should not be considered in the evaluation for image quality).

Ease of use

Each of the following **ease of use** parameters will be rated by the device operator on a 5-point scale (1 = challenging, 2 = somewhat challenging, 3 = neutral neither challenging nor easy, 4 = somewhat easy, 5 = easy), where scores of ≥ 3 are acceptable, as follows:

- Prescribing and Scanning
 - Prescribing PET scan
 - Prescribing MR scans simultaneous with PET
 - Starting and monitoring scanning
 - Reviewing PET and MR image sets
- General Workflow
 - Overall process of doing this exam
 - Performing exam within acceptable duration to meet normal site workflow requirements

Functionality

Each of the following parameters for **functionality** will be rated by the device operator on a binary (Y/N) scale, as follows:

- Did the system function to view the PET, MR, and/or fused image sets?
- Did the system function to position subject and coils in scanner?
- Did the system function to prescribe and scan this exam? If no, indicate which (PET, MR, and/or fused did not function properly).

If no is indicated for any functionality, the investigator should indicate the reason in a provided area for comments on the Case Report Form (CRF).

Safety Assessments

The description, severity, and device relatedness of any AE or SAE during the study will be recorded. Subjects will, if necessary, be provided with emergency care. In the event of any device issues, the event will be recorded. Safety reporting will be conducted as described in this protocol.

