10. STATISTICAL METHODS

■ Statistical Hypothesis

No statistical hypothesis is being prospectively tested in this study. As necessary for regulatory submission, additional analyses will be detailed prior to the star to independent reads in the Statistical Analysis Plan (SAP) prepared by the Sponsor's biostatistician.

■ Sample Size Determination

The sample size is based on the Sponsor's engineering determinations of the required number of sample images, and is not prospectively powered to produce statistically powered results. The protocol aims to acquire 30 images using Q Static (Q. MRAC) and 30 images using ZTE. Datasets may include one or both image type, based on clinical availability, to meet these targets. Assuming that 10% of cases will include both types of data and 25% attrition rate due to various causes, this study requires a population (N) such as that:

$$1.1N - (1.10 \times N)(0.25) = 30 \text{ ZTE} + 30 \text{ Q static}$$

Study Title: Clinical Evaluation Of MP26 Features in Adults

Study No: 114.03-2016-GES-0001

To satisfy this requirement, a minimum population size of $N = 72$ is required. This is approximated to $N = 75$, as this number is considered by the Sponsor to be sufficient to account for unforeseen contributions to dropout or evaluable image rates.

■ Statistical Analysis

■ General Statistical Methods

The study data will be presented in tables, listings, and figures. Data will be summarized using descriptive statistics. The descriptive statistics for variables will include mean, standard deviation, median, Q1 and Q3, minimum, maximum, and count. Categorical variables will be described with counts, percentages. If necessary for regulatory submission, additional statistical methods may be employed as detailed in the Statistical Analysis Plan (SAP) prepared by the Sponsor's responsible biostatistician and stored in the study's clinical history file (CHF).

■ Analysis Set(s)

The study analysis sets include the Safety Population and Per-protocol population.

The safety population includes all subjects enrolled and scanned, the per-protocol population include all subjects enrolled, scanned, processed with ZTE and/or Q-static and without critical protocol deviation.

■ Analysis of Primary Endpoint(s)

General descriptive statistical methods will be used to summarize the study diagnostic image quality results by reader and overall.

■ Analysis of Secondary Endpoint(s)

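### Does the Q.Static arm need a named reconstruction and a gated versus non-gated comparison before its image-quality score can be used?

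*Combined protocol and SAP*

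**What the plan says.** Section 5 (ZTE MRAC and Q Static (Q. MRAC) PET/MR Scanning Procedure) asks that "the site should conduct 5 non-gated MRAC acquisitions and 5 gated acquisitions for each subject around the lung/abdominal region including the diaphragm". The same paragraph adds: "The device operator will save the images and raw data". Under Activities after PET/MR Scanning, all images go to the sponsor or its delegate "for investigational post-processing with the investigational technology prior to image reads".

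Section 6 has two image ratings, both at the level of the subject's whole set:

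- Independent readers give one 5-point score, with 3 or above counted as acceptable: "Scores should be based on the entire image set, considering all available views".
- The site gives one yes/no answer by consensus: "Scores should be based on all views included in the image set, considering all available views".

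Both ratings leave out the LAVA sequence used for attenuation correction.

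The primary objective in Section 3 is to demonstrate diagnostic image quality. It names no comparator. Section 10 states that no hypothesis is tested and plans only this for the primary endpoint: "General descriptive statistical methods will be used to summarize the study diagnostic image quality results by reader and overall". On numbers, Section 4 says "the remaining 37 subjects will be enrolled to have a Q Static (Q. MRAC) exam", and Table 1 gives 30 to 37 for this scan type.

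**The concern.** Gated and non-gated MRAC acquisitions of the same region in the same subject look like a built-in control. Section 2 describes Q.MRAC as meant to make attenuation correction more accurate, and the results are intended for a 510(k) submission. One would expect the plan to name the PET reconstruction that readers see and to use the non-gated data somewhere. It does neither explicitly.

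Two things could be at stake. If a non-gated reconstruction entered the reader's set, one score would cover a mixture of the feature and its predecessor. And even with a clean set, an acceptable score shows only that the images are usable, not that Q.MRAC made them so.

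**Working it through.** **The plan's own figure.** Section 10 solves 1.1N − (1.10 × N)(0.25) = 60, that is 0.825N = 60, so N = 60/0.825 = 72.73. The protocol states 72 and enrols up to 75. This is a count of image sets with no power or precision target, so it implies no comparison. The count that matters here is the 30 to 37 Q.Static subjects. Applying the sponsor's 25% attrition to 37 gives 37 × 0.75 = 27.75, about 28, used below as the low end.

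**Which images are scored.** The relevant places, side by side:

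- Section 2 defines the feature as quiescent-phase PET with a phase-matched attenuation correction. PET corrected with non-gated MRAC does not fit that description.
- The Synopsis (Procedures/Methods) and Section 5 have images processed with the investigational software, and the resulting images read.
- Section 6 counts a set as evaluable only if that processing succeeded.
- Section 10 (Analysis Set(s)) requires ZTE or Q.Static processing for the per-protocol population.
- Section 6 removes the LAVA attenuation-correction sequence from scoring. If the gated and non-gated MRAC acquisitions are of that kind, as the wording suggests, they are not rated as images in their own right.
- Nowhere is a non-gated PET reconstruction said to be made or read.

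All of these point to the Q.MRAC-processed images. What is missing is one sentence excluding the alternative.

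**What an acceptable score can show.** If 30 of 30 sets score 3 or above, the exact two-sided 95% lower limit is 0.025^(1/30) = 88.4%. That answers the stated objective. It does not isolate the feature. Suppose non-gated reconstructions were themselves acceptable with probability p (assumed, with independence between subjects). Then 30 of 30 would occur with probability p^30 and no Q.MRAC effect at all:

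- p = 0.95: 0.95^30 = 0.21
- p = 0.98: 0.98^30 = 0.55
- p = 0.99: 0.99^30 = 0.74

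So the attribution argument is right as arithmetic. It matters only if someone makes the attribution.

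**What a paired read would add.** The half-width of the 95% confidence interval for the mean paired difference is t(0.975, n−1) × SD/√n. The documents give no SD, so 0.5 to 1.0 points is an assumption.

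| Pairs | t | SD 0.5 | SD 1.0 |
|---|---|---|---|
| 28 | 2.0518 | 0.19 | 0.39 |
| 30 | 2.0452 | 0.19 | 0.37 |
| 37 | 2.0281 | 0.17 | 0.33 |

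If no subject scored worse with gated correction, the upper end of the exact two-sided 95% interval, 1 − 0.025^(1/n), would be 12.3% (0/28) or 9.5% (0/37).

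**What it would cost.** If the primary read serves as the gated half, each reader has 28 to 37 extra reads (56 to 74 for two readers). If both versions are re-read in a separate session to protect the primary read, each reader has 2 × 28 = 56 to 2 × 37 = 74. The non-gated reconstructions would also have to be produced. Saving the raw data makes that plausible, but the protocol does not say it is possible.

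**The case for a change.** The best argument for a change is that the control is nearly free: the scans are already requested, the raw data are kept, and no further subjects or readers are needed. Subjects gain nothing directly from taking part, so acquisitions made in a scan of about 30 minutes ought to have a stated use. Section 6 already tells readers to disregard one sequence, so it is a natural place to name the reconstruction. The non-comparative objective also needs the Q.MRAC image set to be identifiable.

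Some of this stands. No endpoint names the non-gated data, their purpose is not given, and no sentence expressly excludes a non-gated reconstruction. An added line would make the protocol tidier.

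The rest does not carry. The contents of a reader's set are what a blinded image evaluation plan normally fixes, and Sections 3 and 6 assign the reads to such a plan, prepared before they start. That plan and the separate SAP are not in the document reviewed, so the text shows a deferral rather than an omission. Data without an endpoint are not wasted either: the sample size rests on engineering needs, and Section 12 allows de-identified data to be used for engineering development. Finally, a masked 5-point quality score does not measure attenuation-correction accuracy, so the added read would still leave the accuracy aim in Section 2 untested.

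**Conclusion.** No change to the plan is needed. Which reconstruction is scored is a gap that those preparing the reads would fill in the way the protocol already indicates. Leaving out a gated versus non-gated comparison is a fair trade-off in a descriptive study. The comparison would be a new question, estimated to within about 0.17 to 0.39 points under the assumed SD, for 28 to 74 extra reads per reader and reconstructions whose feasibility is inferred.

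This rests on two assumptions: that the image evaluation plan puts the Q.MRAC-processed PET in the Q.Static set, and that the report makes no comparative claim. If a non-gated reconstruction were mixed into the set, the score would describe the mixture, and the documents give no basis for sizing that effect. On the plan as it reads, a score of 3 or above supports saying that Q.Static image sets are diagnostically usable. It does not support saying that Q.MRAC improves on non-gated MRAC, and the protocol does not set out to show that.
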